#### 3.2 Trial Design Rationale

**In November 2020, Genmab decided to discontinue development of enapotamab vedotin but continue to offer treatment to patients already recruited in the present trial. In March 2021**

Document Name: GCT1021-01 Protocol

Document Number: TMF-03326

Version: 11.0

**all but 3 patients had discontinued treatment. The patients still on treatment have been on treatment for at least 7 months, which is considered sufficient time to evaluate efficacy and safety. It was therefore agreed to amend the present protocol (Amendment 10) to reduce data collection going forward. Refer to [Appendix VI](#) and [Table 31](#) for applicable procedures and assessments as of Amendment 10.**

The trial consists of a dose-escalation part with two arms (part I) and a dose expansion part (part II).

Part I of this trial is a FIH, open-label, dose-escalation, safety trial of Axl-specific ADC enapotamab vedotin in a mixed patient population with solid tumors to determine the MTD and the safety profile of enapotamab vedotin.

Part I of this trial includes two arms for identification of the most optimal dosing regimen:

- 1Q3W: Dosing once every 3 weeks.
  - There is broad experience with 1Q3W dosing of ADCs and brentuximab vedotin has received market authorization using this schedule (see Investigator's Brochure).
- 3Q4W: Weekly dosing for 3 weeks followed by one treatment-free week.

■ [REDACTED]

The less frequent dosing-arm (1Q3W) is designed as a Modified Bayesian Continuous Reassessment Method (mCRM) incorporating Escalation with Overdose Control (EWOC). This design is considered appropriate as the Bayesian mCRM in general better estimates the MTD with less bias and more precision than a classic 3+3 design. A comprehensive comparison of the Continual Reassessment Method (CRM) to the standard 3+3 dose escalation scheme in phase I dose-finding studies has been described by Iasonos et. al.

The properties of MMAE-based ADCs have been studied comprehensively and based on the overview provided by Deslandes (in particular Table 1 of the article), an U.S. Food and Drug Administration (FDA) analysis of ADCs, in combination with sponsor's own development experience with tisotumab vedotin (HuMax-TF-ADC) it is assumed that the MTD will be between 1.8 mg/kg – 2.5 mg/kg for the 1Q3W dose schedule.

The design provides flexibility in terms of cohort sizes (allowed to vary in CRM but not in classic 3+3 design).

In contrast, the more frequent dosing-arm (3Q4W) will be conducted as a classic 3+3 design as it consists of fewer dose-levels 5-6 and will include fewer patients (15-36, 17 expected as compared to 28 in the 1Q3W-arm). The CRM would need at least ~20-25 patients in order to work properly.

The 3Q4W-arm will follow the 1Q3W-arm. Decisions in this arm will be supplemented by information from the 1Q3W-arm which at all times will have exposed patients at higher dose-levels than the 3Q4W-arm.

The aim of the expansion part is to provide further data on the safety, tolerability, pharmacokinetic (PK) and anti-tumor activity of the selected dose(s)/treatment regimen(s).

Document Name: GCT1021-01 Protocol

Document Number: TMF-03326

Version: 11.0

---

### 3.2.1 Rationale for PK Sampling

The PK sampling described in Section 8.2 is designed so that an adequate estimation of the PK profile, including population PK modelling and non-compartmental estimation of PK parameters, can be performed. It is based on the predicted PK-profiles presented in [REDACTED] where more details can be found.

In the escalation part PK assessments are made only on odd-numbered cycles (please refer to Table 12 and Table 13): a more frequent sampling scheme every two cycles can be more efficient and informative than a less frequent sampling scheme performed every cycle. Performing the current sampling scheme every cycle would not provide additional significantly valuable information compared to the current design.

In the expansion part PK assessments are collected as outlined in Table 14. Of particular interest are the assessments made on Days 1 and 4 in order to obtain samples near the expected  $C_{max}$  for the ADC and MMAE in the 1Q3W arm. In the 3Q4W arm, the corresponding assessments are made on Days 15 and 17.

### 3.2.2 Rationale for Biomarker Analyses

Biomarker samples will be collected to correlate Axl expression as measured by IHC [REDACTED] to clinical response to enapotamab vedotin.

[REDACTED]

### 3.3 Dose Rationale

[REDACTED]

Data from cleavable MMAE-based ADC described in literature, including brentuximab vedotin, glembatumumab vedotin, ASG-5ME-ADC, PSMA-ADC, pinatuzumab vedotin, polatuzumab vedotin and the sponsor compound tisotumab vedotin (HuMax-TF-ADC) have indicated the MTD and/or Recommended Phase 2 Dose (RP2D) are within the range of 1.8 mg/kg to 2.5 mg/kg across the molecules when three-weekly dose schedules were used, for more details please refer to the

Document Name: GCT1021-01 Protocol

Document Number: TMF-03326

Version: 11.0

---

### Investigator's Brochure.

The 1Q3W dose escalation part of this trial includes 7 main dose levels: 0.3, 0.6, 1.0, 1.5, 2.0, 2.4 and 2.8 mg/kg, corresponding to the following dose increments: 100%, 67%, 50%, 33%, 20% and 17%. For the 1Q3W schedule, the MTD and RP2D were determined to be 2.2 mg/kg.

The 3Q4W dose escalation part of the trial is expected to include 5 to 6 dose levels: (0.45), 0.6, 0.8, 1.0, 1.2 and 1.4 mg/kg, corresponding to the following dose increments: (33%), 33%, 25%, 20%, and 17%. The dose level 0.45 mg/kg may be added as described in Section 5.1. There are at least two ADCs containing MMAE as toxin, ASG-5ME and brentuximab vedotin for which a MTD of 1.2 mg/kg has been reported for 3Q4W dosing, for more details please refer to the Investigator's Brochure. Therefore, it is considered safe to apply dose increments higher than 20% (but no more than 33%) for dose levels below this reported MTD for 3Q4W dosing. The increments of the dose escalation steps in the 3Q4W-arm below 1.2 mg/kg are in the range of 33%-20% based on a modified Fibonacci approach and beyond 1.2 mg/kg not higher than 20%. As an additional precaution, the Data Monitoring Committee (DMC) can recommend intermediate dose levels at any step during dose escalation. For the 3Q4W schedule, the MTD was determined to be 1.0 mg/kg.

### 3.3.1 Rationale for Dose Frequency

In the dose escalation part, enapotamab vedotin will be administered 1Q3W in the first dose escalation arm and 3Q4W in the second dose escalation arm; for further details see Section 3.2. The dosing frequency is based on toxicokinetic and toxicology data obtained in cynomolgus monkeys, suggesting adequate recovery of neutrophils, thrombocytes and red blood cell parameters and otherwise an acceptable safety profile. No relevant accumulation of enapotamab vedotin or MMAE between cycles is anticipated based on the proposed dose intervals and non-clinical population PK model (see [REDACTED]).

### 3.4 Number of Patients and Sites

In total, approximately 426 patients can be enrolled in this trial. Assuming an anticipated screen failure rate of 30%, up to 609 patients can be screened.

Up to 41 patients are planned to be enrolled in the 1Q3W dose escalation.

Between 15 and 36 patients are planned to be enrolled in the 3Q4W dose escalation depending on the number of dose levels during the dose escalation.

In the expansion part, approximately 349 patients can be enrolled in 8 cohorts:

In Cohorts 1, 3, 4, 5 and 7, the aim is to enroll 22 patients per cohort; however, in order to obtain evaluable fresh tumor biopsies from at least 15 patients per cohort, up to 15 patients may be additionally recruited per cohort leading to a maximum of 37 patients enrolled per cohort.

Document Name: GCT1021-01 Protocol

Document Number: TMF-03326

Version: 11.0

An efficacy signal has been observed in NSCLC patients without EGFR/ALK mutations, therefore up to 60 additional patients will be enrolled into the NSCLC Cohort 2 (Table 1) to further understand the safety, tolerability, efficacy and biomarker findings of enapotamab vedotin in this population of patients; the aim is therefore to enroll a total of up to 82 patients in Cohort 2. [REDACTED]

A sub-group of the patients in Cohort 2 (up to 30 patients), may be enrolled on a dose of 1.8 mg/kg to further understand the tolerability profile and to extend the therapeutic window of enapotamab vedotin. Enapotamab vedotin belongs to valine-citrulline-monomethyl auristatin E (vc-MMAE) class of ADC, and peripheral neuropathy is a known side-effect of MMAE and a potential dose limiting toxicity (DLT). It has been shown in a pooled time-to-event analysis across eight vc-MMAE ADCs, that peripheral neuropathy events (Grade  $\geq 2$ ) were higher in patients with higher ADC exposure. The MTD/RP2D in ADC-vc-MMAE ranges from 1.8 mg/kg to 2.4 mg/kg. Given the identical cytotoxic payload of MMAE and the similar safety profile observed for enapotamab vedotin as compared to other ADC-vc-MMAEs, 1.8 mg/kg dose is expected to have a better tolerability profile. [REDACTED]

Furthermore, if considered necessary (as assessed by the DMC and the sponsor safety committee) selected cohort(s) might be explored on both dosing schedules from the dose escalation without increasing the total number of patients to be included in the trial.

In Cohort 6, 30 patients with solid tumors (except for NSCLC, melanoma, sarcoma, and ovarian cancer patients, unless having a known AXL gene amplification) who have failed a PD-1/PD-L1 inhibitor and are able to provide the required fresh tumor biopsy will be enrolled.

For further exploration of the safety and efficacy profile of the 3Q4W schedule, patients in Cohort 6 will be enrolled on a dose of 1.0 mg/kg administered 3Q4W, which was determined to be the MTD for this schedule in the dose escalation part of the trial. Preferably, no more than 8 patients should be recruited for one tumor type in this cohort

In order to obtain sufficient evaluable fresh tumor biopsies up to 15 additional patients may be recruited to Cohort 6 to ensure that 25 fresh biopsies are acquired. A maximum of 45 patients may therefore be enrolled into Cohort 6. A higher number of biopsies are required in this cohort due to the mixture of tumor types being enrolled.

Cohort 8 will further explore the safety and efficacy of the 1.0 mg/kg 3Q4W schedule in NSCLC patients without EGFR/ALK mutations. [REDACTED]

Cohort 8 will include up to [REDACTED]

Document Name: GCT1021-01 Protocol

Document Number: TMF-03326

Version: 11.0

37 patients with the aim to collect evaluable fresh tumor biopsies from 15 patients. Recruitment is not linked to the number of biopsies collected and may continue up to a maximum of 37 patients even if 15 fresh tumor biopsies have already been obtained. The benefit/risk balance will be evaluated on an ongoing basis in this cohort. An enapotamab vedotin dose of 1.0 mg/kg administered 3Q4W was well tolerated in the dose escalation part of this trial and was determined to be the 3Q4W MTD. Emerging data indicates that more frequent dosing has the potential to be efficacious when used for ADCs. For example, enfortumab vedotin 1.25 mg/kg 3Q4W demonstrated a clinically meaningful response rate (ORR of 44%) with a manageable and tolerable safety profile in patients with locally advanced or metastatic urothelial carcinoma who were previously treated with platinum and anti-PD-1/L1 therapies. In addition, a phase I/II study of glembatumumab vedotin in patients with advanced melanoma showed a modest improvement in ORR with more frequent dosing schedules compared to the 1Q3W schedule although the number of patients treated was small and no improvement in PFS was observed.

Overall, the 1.0 mg/kg 3Q4W schedule is anticipated to provide a favorable balance of anti-tumor activity with an acceptable safety profile.

An interim analysis for futility will be performed after 22 patients per cohort (minus Cohorts 6 and 8) if there are < 15 patients with evaluable fresh biopsies in the corresponding cohort. If too few responders are observed, further recruitment to the corresponding cohort may be stopped, refer to Section 10.7 for more details. However, if the required number of biopsies as well as responders (see Table 1) have been observed before the futility analysis in the corresponding cohort, the futility analysis can be cancelled.

**Table 1. Overview of sample sizes in the expansion part cohorts**

Cohort number	Minimum number of patients	Stop for futility if $\leq n$ responders/ N patients	Extra patients if not 15** evaluable fresh biopsies from the first 22 patients and no stopping due to futility	Maximum number of patients
1	22	2/22	Up to 15	37
2	22	2/22	Up to 60*	82
3	22	2/22	Up to 15	37
4	22	2/22	Up to 15	37
5	22	2/22	Up to 15	37
6	30	-	Up to 15	45
7	22	3/22	Up to 15	37
8	-	-	-	37
Total	162	-	-	349

\* Enrolment will continue until sufficient data have been generated to confirm initial efficacy, safety, and biomarker findings.

\*\* For Cohort 6: up to 15 extra patients if not 25 evaluable fresh biopsies from first 30 patients.

Document Name: GCT1021-01 Protocol

Document Number: TMF-03326

Version: 11.0

For the dose escalation part 1Q3W, 3 sites will be opened and when the 3Q4W dose escalation is to be initiated, 3 additional sites may be opened. A communication plan for information sharing between sites as well as sponsor will be completed before trial start.

For the expansion part of the trial, up to 60 sites can be opened.

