### 10.2.3 Expansion Part

The results from the expansion phase will be presented using summary statistics. For each cohort,

Document Name: GCT1021-01 Protocol

Document Number: TMF-03326

Version: 11.0

---

the number of responders will be evaluated. Let  $\pi_{response,i}$  denote the proportion of responders in cohort  $i$ , where  $i=1, 2, 3, 4, 5$  or  $6$ . The null hypothesis  $H_{0,i}: \pi_{response,i} \leq 0.10$  will be tested against the one-sided alternative hypothesis  $H_{alt,i}: \pi_{response,i} > 0.10$ , for Cohorts 1-6 and Cohort 8, using the exact binomial test on the 5% significance level, for both confirmed as well as unconfirmed response. The null hypothesis for the platinum-resistant ovarian cancer patients in Cohort 7  $H_{0,7}: \pi_{response,7} \leq 0.15$  will be tested against the one-sided alternative hypothesis  $H_{alt,7}: \pi_{response,i} > 0.15$ . Patients receiving different dosing regimens will be analyzed separately from each other.

With a minimum follow up of at least 7 months for all patients, the analysis per CSR cutoff is considered the full efficacy results. Any data collected after the CSR cutoff will be presented in data listings in the CSR addendum.

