**Table 29. Power Analysis of the Expansion Part**

$H_0$	$H_{alt}$	Power N=22	Power N=30	Power N=37	Power N=45	Power N=82	Power N=202	Power N=349
0.10	0.25	48%	65%	74%	83%	97%	100%	100%
	0.30	69%	84%	91%	95%	100%		
	0.35	84%	94%	97%	99%	100%		
	0.40	93%	98%	99%	100%	100%		
0.15	0.25	30%	33%	45%	45%	69%	97%	
	0.30	51%	57%	71%	74%	93%	100%	
	0.35	70%	78%	88%	91%	99%		
	0.40	84%	91%	97%	98%	100%		

Power=  $P(\text{reject } H_0 | H_{alt})$ , no stopping in interim analysis, calculated using PROC POWER.**Table 30. Operating characteristics in the futility analyses (stop recruiting if  $\leq 2/22$  or  $\leq 3/22$  responders)**

ORR to beat ( $H_0$ )	$H_{alt}$	P[Stop early   $H_0$ ] (N=22)	P[Stop early   $H_{alt}$ ] (N=22)	Statistical Power (N=22+8)	Statistical Power (N=22+15)	Statistical Power (N=22+60)
Stop if $\leq 2/22$ responders						
0.10	0.25	0.62	0.06	65%	73%	92%
0.10	0.35	0.62	0.006	94%	97%	99%
0.15	0.25	0.34	0.06	33%	45%	67%
0.15	0.35	0.34	0.006	77%	88%	99%
0.20	0.25	0.15	0.06	11%	11%	22%
0.20	0.35	0.15	0.006	49%	55%	88%
Stop if $\leq 3/22$ responders						
0.15	0.25	0.57	0.16	33%	44%	63%
0.15	0.35	0.57	0.025	77%	88%	97%
0.20	0.25	0.33	0.16	11%	11%	21%
0.20	0.35	0.33	0.025	49%	56%	87%

The estimates in [Table 30](#) are based on 120000 simulations of clinical trials with the corresponding stopping rule for futility incorporated in the interim analysis. The one-sided test in the final analysis is performed on the 5% significance level.

Document Name: GCT1021-01 Protocol

Document Number: TMF-03326

Version: 11.0

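### Cohort 2 enrolment may end anywhere from 22 to 82 patients on a judgement that includes efficacy, so the fixed-N one-sided 5% response test has no guaranteed level

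*Protocol*

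**What the plan says.** Protocol Table 1 lists Cohort 2 with at least 22 patients, a futility limit of 2 responders in 22, up to 60 extra patients and a maximum of 82. The footnote to the 60 reads: "Enrolment will continue until sufficient data have been generated to confirm initial efficacy, safety, and biomarker findings". Section 3.4 gives the reason for the extension: "An efficacy signal has been observed in NSCLC patients without EGFR/ALK mutations, therefore up to 60 additional patients will be enrolled". It puts the size as follows: "the aim is therefore to enroll a total of up to 82 patients in Cohort 2". By contrast, the extra patients in Cohorts 1 and 3 to 7 are tied to the number of evaluable fresh biopsies.

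Section 10.2.3 sets the null response rate for Cohort 2 at no more than 0.10. It "will be tested against the one-sided alternative hypothesis" of a rate above 0.10, "using the exact binomial test on the 5% significance level, for both confirmed as well as unconfirmed response". Dosing regimens are analysed separately, and up to 30 of the 82 patients may receive 1.8 mg/kg (section 3.4).

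Tables 29 and 30 give operating characteristics for fixed final sizes only; for the extended Cohort 2 these are N=82 and 22+60. The note under Table 30 states: "The one-sided test in the final analysis is performed on the 5% significance level". The only interim rule modelled is futility.

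SAP section 15.1 presents response by summary statistics. SAP section 4.9, which lists changes from the protocol, does not withdraw the test.

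**The concern.** An exact binomial test holds its level when N is chosen without reference to the responses being counted. Here the end of enrolment rests partly on efficacy. Scans are read locally in an open-label trial, so the responses are visible to those who judge whether the data suffice. If favourable response data can end enrolment, the test is in effect taken at a favourable N. Its false-positive rate can then exceed 5%, and the response rate observed at that point tends to be too high.

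The futility rule does not remove the problem. It acts only on low counts, section 3.4 says recruitment may (not must) stop, and the analysis can be cancelled.

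Cohort 2 carries the declared efficacy signal and is the stated background for Cohort 8. A reader shown a Cohort 2 p-value below 0.05 would take the error rate to be at most 5%, which the plan does not secure.

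**Working it through.** **Inputs.** Null rate 0.10, one-sided 5%, exact binomial (section 10.2.3). N from 22 to 82 and futility at 2/22 or fewer (Table 1). Up to 30 patients at 1.8 mg/kg (section 3.4). The number of looks, the reading lag and the accrual rate are not in the documents, so they are varied below.

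**Step 1: reproduce the plan's figures.** The critical value r(n) is the smallest r with P(X ≥ r | n, 0.10) ≤ 0.05.
- n=22: r=6, actual level 1.8%. Power is 48% at a true rate of 25% and 69% at 30%, as in Table 29 and section 10.9.2.
- n=82: r=14, actual level 3.2%. Power is 97% at 25%, as in Table 29.
- Stop at 2/22 or fewer: probability 0.62 at a rate of 10% and 0.06 at 25%; power 92% for 22+60, as in Table 30.

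The test modelled here is therefore the sponsor's test.

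**Step 2: stop at the first significant count, zero lag.** The running count is followed patient by patient at a true rate of 0.10. A false positive is recorded the first time the count reaches r(n) at a look.

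| Looks | Futility ignored | Futility enforced |
|---|---|---|
| Fixed N=82, one test | 3.2% | 2.7% |
| 22 and 82 | 4.5% | 4.0% |
| 22, 52, 82 | 5.8% | 5.1% |
| Every 10 from 22 | 8.1% | 7.0% |
| Every 5 from 22 | 10.1% | 8.8% |
| Every patient, 22–82 | 11.8% | 10.0% |

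In the false positives under per-patient looks the observed response rate averages 22%, against 18% for false positives at fixed N=82; the true rate is 10%.

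**Step 3: allow for unread patients.** The first post-baseline scan is at 6 weeks (section 8.4.7), and confirmation needs a repeat at least 4 weeks later (section 10.4). Every exposed patient belongs to the Full Analysis Set (section 10.1.1), which the SAP uses for efficacy. Patients enrolled but unread when the count crosses r(n) therefore enter the final test. Looks are per patient and futility is ignored; the overrun sizes are assumptions.

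| Unread patients at crossing | Enrolment stays closed | Enrolment resumes if the matured test fails |
|---|---|---|
| 0 | 11.8% | 11.8% |
| 5 | about 6.2% | about 7.8% |
| 10 | about 5.4% | about 6.6% |
| 15 | about 5.1% | about 6.0% |

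**Step 4: split by regimen.** If 30 patients receive 1.8 mg/kg, the 2.2 mg/kg test has at most 82 − 30 = 52 patients. Per-patient looks with zero lag then give 8.7% (8.1% with futility enforced). A fixed-N test of the 30 patients at 1.8 mg/kg has level 2.6%. The chance of a false positive in either regimen is 1 − (1 − 0.0873)(1 − 0.0258) = 11.1%.

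**Step 5: a level that would hold.** For per-patient looks from 22 to 82 with zero lag, a nominal p ≤ 0.0175 at each look gives 4.6% overall. For looks at 22, 42, 62 and 82, a nominal 3% gives 4.5% overall, with power 95.7% at a true rate of 25%.

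**The case against.** The strongest reply is that the footnote is not an efficacy stopping rule. It speaks of sufficient data on efficacy, safety and biomarkers together, and no document describes repeated significance testing. That is right. A reader might infer that enrolment stops once the test is significant, or that the true error rate is 12%; the documents support neither. The 11.8% needs a look after every patient, instant reading and no further patients once the boundary is crossed. The scan schedule and up to 60 expansion sites make zero overrun implausible.

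The consequence is also limited. The protocol calls the trial exploratory and not formally powered, its primary endpoints are DLTs and adverse events, and the recommended dose rests on an overall clinical assessment. The SAP's efficacy table list names no binomial test, and development has been discontinued. The test was not withdrawn, however: protocol version 11.0 still carries it, and SAP section 4.9 is silent on it.

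Finally, a split around the extension largely exists. SAP section 4.4 plans subgroups by inclusion before or after Amendment 6, with confirmed response in a forest plot. The extension was written into Amendment 5, an internal version, so Amendment 6 was the next one issued. This stands, and no new analysis is needed for that purpose.

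**Conclusion.** The point holds in a limited form. The plan leaves the end of Cohort 2 enrolment to a judgement that includes efficacy and then claims a fixed-N 5% level, so that level is not guaranteed. The size of the departure cannot be fixed from the documents. At a true response rate of 10% it runs from none (3.2% at fixed N=82, 4.5% with looks only at 22 and 82), through about 5–8% with frequent looks and 5 to 15 unread patients, to a ceiling of 11.8%. For 2.2 mg/kg alone the zero-lag ceiling is 8.7% if 30 patients receive 1.8 mg/kg. These figures assume that a significant count would end enrolment, which the footnote permits but does not state. They leave out the further multiplicity from testing both confirmed and unconfirmed response.

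**What to change.** Enrolment is complete, so N can no longer be fixed prospectively; the remedy lies in analysis and reporting.

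1. State how and when Cohort 2 enrolment ended, for each dosing regimen, and whether response data played a part.
2. Unless N was fixed without using response data, report the response rate with an exact confidence interval and label the binomial p-value descriptive, with no 5% claim. Alternatively, if the looks taken are documented, test at a reduced nominal level set for them, for example p ≤ 0.0175 for per-patient looks from 22 to 82 (4.6% overall).
3. Use the Amendment 6 subgroup already in SAP section 4.4 to show the Cohort 2 response rate before and after the extension, next to the pooled rate. Amendment 6 also changed some expansion eligibility criteria, so the two periods may differ for that reason too.

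The cost is wording in the SAP and report and a rearranged table. The sponsor gives up an unqualified 5% significance statement for Cohort 2.
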